#### **4.2.1 Approximate Number of Subjects**

Approximately 135 Geisinger subjects (65 patients and 50 caregivers) will participate in the study. Patients are able to participate independent of having a caregiver; therefore the number of Geisinger patients enrolled is reflective of this possibility. Our goal is to include 100 participants in our analysis (50 patients and 50 caregivers) organized as 25 Cases Dyads and 25 Control Dyads. We will enroll 20 Geisinger providers in the treatment site who will participate in this study. If a caregiver receives care at Geisinger, his/her patient-related records are not of interest to or related to this study.

Background Logic Regarding Sample Size: The number of eligible lung cancer patients was estimated from a twelve-month report (May 2016-April 2017) ("Estimate Time Period") from each respective hospital which informed the Exploratory Evaluation Study design. Patients were included if, during the Estimate Time Period, they had an active lung cancer diagnosis on the EHR problem list and had an encounter at one of the following oncology departments (Hematology Oncology Danville, Radiation Oncology Danville, Hematology Oncology GWV, Radiation Oncology GWV) ("Inclusion Criteria"). There were 153 eligible patients from GMC ("GMC Lung Cancer Patients"), 137 eligible patients from GWV ("GWV Lung Cancer Patients"), and 21 eligible patients from GCMC ("GCMC Lung Cancer Patients") for potential inclusion in the Exploratory Evaluation Study and Phase III FCA expansion rollout. Given that the Exploratory Evaluation Study period is 6 months, the estimated count of eligible patients is reduced by 50% to 77 Case patients at GMC, 69 Control patients at GWV and 11 Control patients at GCMC.

Based upon Phase II enrollment at GMC, it is anticipated that 37% of eligible GMC Lung Cancer Patients (i.e., 28) will consent to participate in the evaluation and enroll as a Dyad. Based on Phase II enrollment at GMC, 100% of these patients will identify a caregiver who consents to

*Version 1.10 – 5.24.2018*

participate as part of a dyad. Based on Phase II observations, 90% of these Dyads (i.e., 25) will complete an intensive 8-week treatment cycle. Recognizing variability in the incidence of disease, we chose the more conservative sample size of 25 patients enrolling in the study as part of a dyad for each arm thus resulting in 25 Case Dyads and 25 Control Dyads or 100 patient-caregiver participants. Based on Phase II observations, 90% are estimated to complete the 8-week treatment cycle and study.

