***Observe FCA in clinical oncology practice to evaluate quality and performance indicators.***

Integrate exposure to FCA as standard of care in a conveniently selected clinic for persons with lung cancer and their caregivers. Clinicians in this clinic have contributed to the development and testing of FCA as standard of care at Geisinger Medical Center in Danville, PA (“GMC”). This clinic will serve as the treatment site. Electronic health records and FCA dashboard analytics will be used to evaluate clinician use of the tool. Clinicians at the treatment site will provide interview data describing their experience related to quality, FCA adoption and implementation into workflow integration at the post-period;

### 3.2 Specific Aim 2

***Observe FCA use among patients and caregivers to evaluate quality and performance indicators associated with oncology care.*** From the treatment site, identify, recruit, consent and enroll persons with lung cancer (newly diagnosed or recent recurrence of disease) and their caregivers. Recruitment will continue until 25 patients and 25 caregivers (Case Dyads) are enrolled. Electronic health records for patients (appointment, clinical, and patient-reported data such as the M.D. Anderson Symptom Inventory that is standard of care) and study questionnaires will be used to evaluate quality and performance indicators. Questionnaires will be fielded with Case Dyads, as hereinafter defined, at baseline and after 8 weeks of exposure to FCA. Pre-post changes will be evaluated among cases.

### 3.3 Specific Aim 3

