***Observe quality and performance indicators among usual oncology care in similar patient-caregiver population to compare with cases.*** From non-treatment sites, identify, recruit, consent, and enroll persons with lung cancer (newly diagnosed or recent recurrence of disease) and their caregivers into the evaluation study. Recruitment will continue until 25 patients and 25 caregivers are enrolled (Control Dyads). Electronic health records for patients (appointment, clinical, and patient-reported data such as the M.D. Anderson Symptom Inventory that is standard of care) and study questionnaires will be used to evaluate quality and performance indicators however, questionnaires will be fielded at the post-period only. Non-treatment sites will not provide FCA as standard of care and function as control sites. These sites will include Geisinger Wyoming Valley in Wilkes-Barre, PA (“GWV”), and Geisinger Community Medical Center in Scranton, PA (“GCMC”). A case-matched controlled design will be used to evaluate differences in quality and performance indicators between groups at the post-period only.

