For every Case patient enrolled at GMC, a data analyst will run the algorithm to consume aggregate electronic health record data to find and create a database of potential participants that meet inclusion (and do not meet exclusion) criteria at control sites. A weekly occurrence of the eligibility list will occur however, depending on the rate of recruitment the study team will determine whether this needs to occur more frequently. Study team members will apply a 1:1 case-matched control strategy to identify potential control patients that match case patients in terms of sex, age category, lung cancer histology, and lung cancer clinical and/or pathological staging information. This will be done after the Case patient-participant has a Case caregiver-participant consented to ensure that Case Dyads are enrolled and available for matching. If a Case patient-participant has enrolled but the Case caregiver-participant fails to enroll, the Case patient-participant will still be eligible for the study however the study team will recruit a replacement Case Dyad with the goal of enrolling 25 Case Dyads. Case patient-participants without caregiver-participants will be removed from analyses. Similarly, if a Control patient-participant consents but a Control caregiver-participant fails to enroll, the study team will identify a replacement Control Dyad with the goal of enrolling 25 Control Dyads. Research assistants will use the database to run weekly reports to identify potential control patients at GCMC or GWV to approach for recruitment. The research assistants will verbally review the list of potential participants as well as the weekly MDC list at GCMC and GWV with clinical staff to validate that patients on the list meeting inclusion criteria and can be approached for recruitment. The research assistant will be available to speak with patients before or after their scheduled medical appointments.

For the purpose of study awareness, informational flyers will also be available to patients in the exam rooms, waiting rooms, and through Oncology Care's MDC (**Attachment X: Recruitment Flyer - Controls**).

Demographic information will be collected on all eligible participants who are asked to participate. This information will be collected as part of the Pre-Treatment Survey for Case

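### The analysis goal of 25 dyads per arm equals the number enrolled, yet the protocol expects 90% to complete: about 90 participants, not 100, in the post-survey comparison

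*Combined protocol and SAP*

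**What the plan says.** Section 4.2.1 states the size of the analysed set: "Our goal is to include 100 participants in our analysis (50 patients and 50 caregivers) organized as 25 Cases Dyads and 25 Control Dyads". Section 4.4.2 repeats it.

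Recruitment is governed by enrolment, not completion. For the treatment site, Specific Aim 2 says: "Recruitment will continue until 25 patients and 25 caregivers (Case Dyads) are enrolled". Specific Aim 3 sets the same limit for the control sites.

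The closing paragraph of section 4.2.1 also treats 25 per arm as a number enrolling, and then adds: "Based on Phase II observations, 90% are estimated to complete the 8-week treatment cycle and study".

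Section 4.3 has a replacement rule, triggered when a patient has joined but the caregiver does not. In that event, "the study team will recruit a replacement Case Dyad with the goal of enrolling 25 Case Dyads"; a parallel rule covers controls. Sections 4.2.1 and 4.4.2 plan for 65 patients and 50 caregivers, and explain the extra patients by the possibility that some take part without a caregiver.

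Section 4.8.2 gives a different size, 50 Case Dyads and 50 Control Dyads, and says that power was not estimated.

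**The concern.** The same number, 25 per arm, serves both as the point where enrolment stops and as the number to be analysed, while the protocol itself expects one dyad in ten not to finish. The stated analysis size is therefore not what the plan's own figures deliver.

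The primary question (section 4.6) is a Case-Control difference at the post-period, and much of it rests on surveys. Section 4.8.1 averages the patient and caregiver scores within each dyad, so the loss of either post-survey leaves that average incomplete. Controls are surveyed only at the post-period, so a Control Dyad lost before then supplies no survey data. At stake are an honest statement of how many dyads the main comparison will contain, and a planned account of those that drop out.

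**Working it through.** **Inputs**

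- Eligible patients in six months (4.2.1): "77 Case patients at GMC, 69 Control patients at GWV and 11 Control patients at GCMC".
- Consent (4.2.1): "37% of eligible GMC Lung Cancer Patients (i.e., 28) will consent".
- Completion, first use (4.2.1): "90% of these Dyads (i.e., 25) will complete an intensive 8-week treatment cycle".
- Completion, second use (4.2.1): 90%, applied after 25 per arm has been chosen.
- Enrolment stop (Aims 2 and 3): 25 dyads per arm.
- Analysis goal (4.2.1, 4.4.2): 25 dyads per arm, 100 participants.
- Planned enrolment (4.4.2): 65 patients and 50 caregivers.

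**Step 1. Reproduce the protocol's 25.** Half of the 153 GMC patients seen in twelve months is 76.5, stated as 77. Then 77 x 0.37 = 28.49, stated as 28, and 28 x 0.90 = 25.2, stated as 25. The chain reproduces, and it shows that 25 starts as a count of completers out of 28 enrolled.

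**Step 2. Apply the second 90% to 25 enrolled.**

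- Per arm: 25 x 0.90 = 22.5 dyads.
- Both arms: 2 x 22.5 = 45 dyads.
- Participants: 2 x 45 = 90, against 100 stated.

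In reverse, expecting 25 completers needs 25 / 0.90 = 27.8, that is 28 enrolled per arm, which is the figure from which the chain began.

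**Step 3. Look for a margin elsewhere.**

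- Patients: 65 - 50 = 15 extra, assigned to patients without a caregiver. Section 4.3 removes such Case patients from the analyses.
- Caregivers: 50 - 50 = 0 extra. A dyad needs a caregiver, so the 15 extra patients cannot make up lost dyads.
- Replacement: triggered only by a caregiver who does not enrol, not by a dyad lost later.

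Nothing closes the gap.

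**Step 4. Effect on precision.** With equal arms and a common standard deviation s, the standard error of a difference in means is s x sqrt(2/n). The ratio for 22.5 against 25 per arm is sqrt(25 / 22.5) = 1.054, about 5% wider.

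**Step 5. Sensitivity to the 90%.** The rate comes from Phase II, which section 2 describes as twelve dyads; one dyad there is 1/12 = 8.3 percentage points. Taking an assumed range:

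| Completion | Dyads per arm | Participants |
|---|---|---|
| 85% | 25 x 0.85 = 21.25 | 85 |
| 90% | 22.5 | 90 |
| 95% | 25 x 0.95 = 23.75 | 95 |

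Only 100% completion gives 100.

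**The case against.** The strongest defence is that 100 is an approximate goal in an exploratory study. Sections 4.8.1 and 4.8.2 call the tests descriptive and say that no power was estimated, so no inference depends on reaching 100. The 90% stands in the same section, where any reader can see it. This bears on weight: the consequence is modest. It does not remove the inconsistency, because the stopping rule and the completion rate together do not lead to the goal.

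A second defence is that 25 was meant net of loss, since it was derived that way. But section 4.2.1 and both Aims describe the 25 as enrolled, and the 90% is applied after that choice.

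A third is that survey loss is not total loss. This stands. The table in section 4.6 includes outcomes from Epic and Aria, such as survival, symptom inventory scores, missed appointments and admissions, and these may be available for patients who never return the post-survey. Non-completing Case Dyads may have baseline surveys. Section 4.8.1 also plans separate patient and caregiver comparisons, to which one remaining member could contribute. The figure of 90 therefore applies to the post-survey comparison of dyads, not to every endpoint.

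Finally, three follow-up attempts are planned for non-responders. They may limit non-response, but the 90% is the protocol's own estimate and is not stated to be before reminders.

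**Conclusion.** The point holds. On the protocol's own figures, the post-survey comparison would contain about 22 to 23 dyads per arm, 45 dyads and 90 participants in all, rather than 25 per arm and 100. The standard error would be about 5% larger. This assumes that the 90% applies equally in both arms and that 25 dyads per arm are actually enrolled; an assumed completion of 85% to 95% gives 85 to 95 participants.

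Three stronger conclusions might be inferred, and the documents do not support them.

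- *Only about 20 matched pairs would remain* (25 x 0.9 x 0.9 = 20.25, if losses are independent). Matching is a recruitment step in section 4.3. Section 4.8.1 plans unpaired tests between groups, and no rule drops a dyad whose match is lost. The figure does not belong in the analysis goal.
- *Those who complete will be the healthier dyads, so the comparison is biased.* This is possible in a serious disease, but the documents give no reasons for the expected loss and no sign that it would differ by arm.
- *The study becomes underpowered.* There is no power target to miss.

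**What to change.** - Keep enrolment at 25 dyads per arm. In sections 4.2.1 and 4.4.2, restate the post-survey analysis goal as about 22 to 23 completing dyads per arm, about 90 participants, and label 25 consistently as the number enrolled.
- Reconcile section 4.8.2, which gives 50 Case and 50 Control Dyads, twice the number per arm found elsewhere. Otherwise a larger conflict remains after the first correction.
- Add to section 4.8.1 that completers will be reported against enrolled, by arm, with reasons for loss, and that record-based outcomes will be reported with their own denominators.

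The cost is protocol wording, a slightly less favourable number, and a short record of why each dyad was lost. No extra patients are needed.

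If the sponsor prefers to keep 100 analysed, the replacement rule in section 4.3 would have to cover dyads lost before the post-survey, with about 28 enrolled per arm. The forecast of 28 at GMC leaves almost no slack for that. At the control sites, (69 + 11) x 0.37 = 29.6, if the GMC consent rate applies there, which is an assumption. Restating the goal is the easier route.

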#### **4.2.2 Inclusion Criteria**

##### **Patients**

- Patients who are 18 years of age or older and diagnosed with lung cancer who 1) are scheduled to start Oncology Care (chemo and/or radiation-therapies) OR 2) on active Oncology Care and recently started within 3 weeks ( $\leq 27$  days)
- Receive care at GMC, GWV, or GCMC
- English-speaking
- Established/intends to establish a MyGeisinger Account (cases only)

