This study is characterized as an exploratory evaluation as the design limits the generalizability of findings and these findings will be biased in several ways. First, the treatment clinic and clinicians have been intimately involved in the development and implementation of the FCA. This factor likely influences clinician adoption of the FCA in care and could be limiting factor in other settings where FCA may be tested. Additionally, sites were conveniently chosen and site-level factors may bias study findings. The administration of the study sites is centralized to infer some consistency with operational procedures however this is a limiting factor in this exploratory evaluation. Quality and performance metrics are not routinely collected in these outpatient settings. In the absence of system-level data to describe variation in care, the study will depend on study questionnaires to evaluate quality and performance, which is a limiting factor as the perspective is contained to the study participants rather than the aggregate patient-population at each site. Secondly, a convenient sample of patients receiving care at the study clinics will be recruited into the study on a first-come, first serve basis and without random assignment to treatment or control groups. Additionally, Case Dyads must enroll in MyGeisinger patient portal to use FCA and although not required for the study, we will encourage Control Dyads to enroll in MyGeisinger patient portal to minimize bias related to health literacy using technology. Another potential bias is that some caregivers may reside out of state and this distance may impact the quality of their relationship with the patient; every effort will be made to match Case and Control Dyads with similar spatial situations but this may be prohibitive given the project timeline. These factors limit the assumption that any observations associated with FCA are related to the treatment use as variation in patient factors or the quality of care at clinics may account for observed associations. Potential participants (patients) are reasonably expected to receive an intense, brief oncology care with multiple appointments thus offering the opportunity to measure the impact of FCA use. Dyads will not be randomly assigned to treatment or control but offered standard of care per the clinic site. The study team will provide hands-on technical assistance to Case Dyads and associated clinicians to facilitate implementation and observe key learnings. Changes from baseline to post-study period will be evaluated within the Case Dyads, but given the severity of the condition and brief study period, the project team expects to observe greater differences in post-study period indicators between Case Dyads vs. Control Dyads.

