##### **Caregiver**

- Recognized/intends to be recognized as proxy for patient's MyGeisinger Account (cases only)
- English-speaking

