## 4.5 Procedures

### Case Dyads:

The research assistant will approach all eligible patients in the clinic (**Attachment U: RA talking points**) to inform them of the FCA study opportunity. Patients will learn about the need to identify a caregiver who can participate in using FCA with them to enroll in the study, however patients can participate in the study regardless of caregiver participation. Also, as part of agreeing to participate the patient will need to have or establish a MyGeisinger account and the caregiver will need to have or establish proxy access to the patients' medical record (some caregivers may already have this access). Interested dyads (patient and caregiver) that agree to participate will provide consent (**Attachment F: Informed Consent - Controls**) and this will be electronically stored in REDCap by the Research Assistant, who will also facilitate access or registration to MyGeisinger for the patient and caregiver. Participants who do not receive a copy of their consent form at the time of consent will be mailed a copy of their consent form for their records (**Attachment BB: Consent Form Letter**).

Prior to enrollment in the Family Caregiver Application, the dyad will be asked to complete a Pre-Treatment Survey (**Attachment A: Pre-Treatment Survey Patient and Attachment B: Pre-Treatment Survey Caregiver**). The terms "Study Questionnaires" and "Surveys" are used interchangeably throughout this protocol and represent the same items. Patients and caregivers will receive unique Surveys. Electronic versions of the consent and survey will be available via REDCap (paper versions available upon request). Patients and caregivers can complete the consent and survey in the clinic at the baseline time point using a secure study device (i.e., study iPad with a secure link populated through REDCap) or in hard copy. When a survey is completed and returned to the study team, the patient and caregiver will each receive a \$25 gift card. The gift card will be mailed to each participant (**Attachment T: Compensation Letter**).

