#### 4.5.1 Study Flow Diagram

## 4.6 Primary Question

The primary endpoint will be difference in quality and performance metrics at the post-period associated with FCA **exposure**, evaluated between the Case Dyads and Control Dyads.

Aggregate means will be calculated for dyads and compared between groups. Sensitivity analyses may stratify these results by low-moderate-high FCA use. FCA exposure is designed to impact care coordination, patient satisfaction, patient and caregiver quality of life, perceived involvement in care, and symptom management, all quality indicators, over standard of care in control clinic sites where care coordination is less efficient, labor-intense, and often frustrating to patients and caregivers. Additionally, the Consumer Assessment of Healthcare Provider Survey, performance metrics, for Cancer Care and Health Information Technology scores for FCA users vs. controls is expected to be greater as controls would have standard of care with no additional enhancements and could utilize MyGeisinger portals.

Theoretical Domain	Parameter of interest operationalized	Perspective	Data sources or location
Quality of Care	
Patient Satisfaction with Service Quality Hospital operations and services; physicians and staff; endorsements for others
 
Family Satisfaction with Advanced Cancer Care Information giving, availability of care, physical care, psychosocial care
	Patient Caregiver	
Patient Survey Attachment A and C: Pre and Post Survey
 
Caregiver Survey Attachment B and D: Pre and Post Survey

Patient-Caregiver Outcomes	
Quality of Life Patient's functional scales, symptoms, financial impact and global health and quality of life ratings
 
Caregiver's own state, relationships, outlook, patient condition, finances, environment
 
Caregiver Burden Personal impact, other family members, medical issues, concerned about loved one
 
Clinical Outcomes Survival, remission, exacerbation, MD Anderson Symptom Inventory
	Patient Caregiver Caregiver Patient	
Patient Survey Attachment A and C: Pre and Post Survey
 
Caregiver Survey Attachment B and D: Pre and Post Survey
 
Caregiver Survey Attachment B and D: Pre and Post Survey
 
Epic EHR See section 4.8.1

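### Portal and proxy access are entry criteria for Cases only, and status at entry is not a listed data element, matching factor or analysis variable

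*Combined protocol and SAP*

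**What the plan says.** Section 4.2.2 sets two criteria that apply to Cases alone. The patient criterion is "Established/intends to establish a MyGeisinger Account (cases only"; the caregiver criterion is "Recognized/intends to be recognized as proxy for patient's MyGeisinger Account (cases only". Controls have no counterpart to either.

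Section 4.1 explains that Case Dyads need the portal in order to use the Family Caregiver Application (FCA). It then states the mitigation: "we will encourage Control Dyads to enroll in MyGeisinger patient portal to minimize bias related to health literacy using technology". The same sentence says that enrollment is not required of Controls.

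Section 4.5 gives Case Dyads practical help. The research assistant takes consent and is the person "who will also facilitate access or registration to MyGeisinger for the patient and caregiver". FCA is activated only after portal access is in place. The Control Dyads part of Section 4.5 does not mention the portal.

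Section 4.3 matches Controls 1:1 so that they "match case patients in terms of sex, age category, lung cancer histology, and lung cancer clinical and/or pathological staging information". Section 4.8.1 compares the arms with univariate tests on post-period surveys. Its patient and caregiver data lists name survey responses, encounters and FCA usage, but no portal-account or proxy field. Section 4.6 includes health information technology (health-IT) scores in the primary question and predicts that "scores for FCA users vs. controls is expected to be greater", while noting that Controls could use the portal.

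**The concern.** The two arms enter under different rules on a characteristic that could plausibly affect several of the outcomes: satisfaction, perceived coordination and health-IT scores. Willingness to set up a portal account, and to have a caregiver act as proxy, may go with engagement and comfort with technology. If so, Cases could score better at the post-period even if FCA did nothing.

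The design offers little protection. Controls have no baseline survey (Section 3.3), the matching factors are demographic and clinical, and the between-arm tests are unadjusted. Section 4.1 justifies the post-only design by expecting the groups to be alike at baseline. That does not fit the same section's account of a technology-related bias between them.

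At stake is how the primary comparison is read. If portal and proxy status at entry are not recorded for Controls, a reader cannot tell how far the arms differed on the one characteristic that the plan itself names as a source of bias.

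**Working it through.** **Step 1. Where portal or proxy status at entry could appear**

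| Place | Cases | Controls |
|---|---|---|
| Eligibility (4.2.2) | has or intends, both roles | no criterion |
| Procedures (4.5) | registration help; access before FCA activation | portal not mentioned |
| Encouragement (4.1) | not applicable (required) | encouraged, not required |
| Matching factors (4.3) | not a factor | not a factor |
| Data elements (4.8.1) | not listed | not listed |
| Between-arm analysis (4.8.1) | not used | not used |

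By the time of FCA activation every activated Case has access. The share of Controls with access, at entry or later, is not given anywhere.

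**Step 2. The plan's own sample figure**

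Section 4.2.1 derives 25 Case Dyads as follows: 153 × 0.5 = 76.5, taken as 77; 77 × 0.37 = 28.5, given as 28; 28 × 0.90 = 25.2, given as 25. This reproduces, and Sections 3.2 and 3.3 also use 25 dyads per arm, so I use 25. (Section 4.8.2 gives 50 dyads per arm, which does not agree with those sections.) The plan states no alpha, power, effect size or SD.

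**Step 3. Precision of the main comparison**

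Assumptions: SD 1, two independent groups, 95% two-sided t interval.

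Half-width = t(0.975, 48) × √(1/25 + 1/25) = 2.01 × 0.283 = 0.57 SD.

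**Step 4. Possible size of the bias**

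The documents give neither portal uptake among Controls nor the relation between portal status and outcome, so both inputs are assumed. If all Cases have access:

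Difference with no FCA effect = share of Controls without an account × score gap.

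- Low: 0.20 × 0.3 = 0.06 SD, and 0.06 / 0.57 = 11% of the half-width.
- High: 0.50 × 0.5 = 0.25 SD, and 0.25 / 0.57 = 44% of the half-width.
- Wider assumptions (10-70% without an account, gap 0.3-0.8 SD): 0.10 × 0.3 = 0.03 SD to 0.70 × 0.8 = 0.56 SD.

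At 0.25 SD, the chance of a nominal two-sided p < 0.05 with no FCA effect, by the normal approximation, is Φ(0.25/0.283 − 1.96) + Φ(−0.25/0.283 − 1.96), about 14% instead of 5%.

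Two features make these figures generous. They attribute the whole score gap to selection. They also count every Control without an account, although a Control who intends to open one would meet the Case criterion.

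**Step 5. Cost of a restricted comparison**

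If half the Controls meet the criterion, about 12 remain:

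Half-width = t(0.975, 35) × √(1/25 + 1/12) = 2.03 × 0.351 = 0.71 SD, against 0.57 SD with all 25.

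**The case against.** The strongest reply is that the plan already discloses this. Section 4.1 names the bias and says that patient and site factors limit attribution of any difference to FCA. Sections 4.8.1 and 4.8.2 call all tests descriptive. That stands, and it limits the consequence. It does not tell a reader how different the arms were, and describing the groups well is a central task of an exploratory study.

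Three stronger readings are tempting, and the documents do not support them.

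- A reader might infer that technology-ready Cases are set against unselected Controls. Cases qualify on intent alone and are helped to register. Controls are matched on four factors and encouraged to enroll.
- A reader might infer that the planned data cannot address the question at all. Survey responses are collected in both arms, the items sit in attachments that are not shown, and study IDs link participants to electronic health record (EHR) data (Section 4.9.1). Indirect examination may be possible. The health-IT scores are a weak substitute, however, because they are measured post-period and treated as an outcome.
- A reader might infer that having an available caregiver is a Case-only selection. Both arms are built around a consenting caregiver, and a Control Dyad is replaced if the caregiver does not enroll (Section 4.3). Only proxy status, or the intent to obtain it, differs.

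It is also fair to say that FCA requires the portal, so part of any portal difference belongs to the exposure being compared with usual care. How much of it to call bias is a choice of estimand. That is a good reason not to replace the main comparison.

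**Conclusion.** The point holds in a limited form. The entry criteria are asymmetric, and the acknowledged bias has only encouragement as mitigation. Because status at entry is not matched on, listed or analysed, the bias can be examined only indirectly. The expectation of no baseline difference is inconsistent with the bias described in the same section.

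The size is unknown. The range of 0.06-0.25 SD rests entirely on assumed uptake (20-50% of Controls without an account) and an assumed score gap (0.3-0.5 SD). It shows that the bias could be anything from negligible to a material part of the 0.57 SD half-width. It does not show that any Case advantage is partly produced by the entry criterion, which a reader might otherwise conclude. This is a cheap improvement to an exploratory study and does not invalidate the comparison.

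**What to change.** For every Control dyad, record at consent, and before any encouragement to enroll:

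- the patient's portal account (has, intends or no, with date);
- the caregiver's proxy access (has, intends or no, with date).

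Take account status from the EHR and intent from one question. An account date might be recovered from the EHR later; intent at consent cannot be, so the fields should be in place before Controls are enrolled. Add both to the data elements in Section 4.8.1 and describe them by arm.

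Report a supplementary Case-Control comparison restricted to Controls who meet the Case portal and proxy criterion, beside the all-Control result and including the health-IT scores. Keep the all-Control comparison as the main result and leave Control eligibility unchanged. Reconcile the Section 4.1 statement on baseline similarity with the bias that the section describes.

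The cost is two fields and one extra comparison. The restricted comparison will be less precise (half-width about 0.71 SD if 12 Controls remain) and breaks the 1:1 matching. It does not remove the confounding of arm with site, since all Cases come from one center and all Controls from the other two.
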